#### Analysis 1:

The first model will include only treatment as a predictor of cancer detection. Levels considered for inclusion in the model will be: case; batch; and centre. To prevent over-fitting, each level will only be included in the final model if it explains a sufficient portion of the variability and improves model fit. Screening centre will be added as a level to the model to account for clustering. It will be retained in the model if it improves model fit (Wald test at the 5% level, see limitations section). Then batch will be considered for addition as a level to this model if it improves model fit according to the same criteria. The treatment will be added to this model.

A sub-analysis of those cases which are intended to be read in the first or last 5 of the batch, younger women  $(\le 52, 53-59, \ge 60)$  and the first batches to be read in a workday (by both readers) will be conducted.

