## 2 Trial Design

#### 2.1 Trial summary

The trial is a multi-centre cluster randomised parallel group superiority trial. The centres will be English Breast Screening centres with digital mammography equipment. The intervention is reversing the order in which the second radiologist reads each batch of mammograms. A cluster for randomisation is a batch of mammograms (circa 30 women's mammograms). The unit for analysis is the individual women's outcome.

The pre-pilot will be conducted in three screening centres for two weeks to ascertain the practical issues with implementation, and to test the Crystal report for data extraction. Concurrently a survey of all English breast screening centres will be conducted to ascertain key characteristics relevant to the trial which may differ between centres, such as the blinding of one reader to another's decision, and the method of arbitration used.

The trial will be implemented using an adaptation to the NBSS software used at participating centres.

The trial will last 16 months in 44 centres (1.5 million women). The first 12 months data (1.1 million women) will be collected from the NBSS database to determine whether the intervention affected cancer detection rate.

The full data set will be collected three years after the end of the study, to ascertain whether there was a decrease in rate of interval cancers (cancers presenting symptomatically in the three years after screening), and therefore whether the intervention reduced the number of cancers missed at screening.

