## 3.4 Statistical Analysis Plan

## i) Primary

To determine whether cancer detection rate is higher in the intervention group in comparison to the control group analysis will be conducted using a multi-level logistic regression model.

Levels to be included in the model are case, batch, and centre. To prevent over-fitting each level will only be included if they explain a sufficient portion of the variability.

It is reasonable to expect characteristics at the level of the women screened to be very similar between intervention and control due to the large number of batches of women randomised. Similarly centre level characteristics such as the arbitration system used will not differ between intervention and control as randomisation is at the batch level within each centre. Therefore the main analysis will simply contain one predictor, intervention or control arm. The intervention will be considered effective if the 5th percentile of the distribution of the coefficient for the intervention in the model is greater than zero.

A second analysis will be conducted including adjustment for characteristics of the woman screened (age and whether they have previously attended screening). Sub-group analysis will be conducted in younger women, those whose cases are read at the beginning or end of the batch, and younger women, as the intervention may be more effective in these groups.

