#### 2. Power and Sample Size

Currently, 14,700 cancers are detected by screening each year and the cancer detection rate is 7.8 per thousand women screened. (NHS Information Centre, 2012) To detect one extra cancer per 2000 women screened, this would increase the cancer detection rate to around 8.3 cancers per 1000 women screened. To detect this change of 0.5 cancers per 1000 women, for a two-tailed test at 80% power and 5% significance, 501,361 women are required in each arm, see figure 1.

However, as randomisation occurs at the batch level, collected data is clustered and must also be taken into consideration. The sample size of a clustered study must be increased by the Design Effect (DE), which is calculated as  $DE = 1 + (m - 1)\rho$  for a given ICC ( $\rho$ ) and cluster size (m).

ICC was calculated from previous data, using a logistic binomial-Gaussian model (method B) with 1000 Monte Carlo simulations. (Goldstein, 2002) Hence, using the derived ICC of 0.002 and a cluster (batch) size of 40 women, this then gives the DE as 1.09.

Therefore, the overall sample size required is for 1,093,780 women, or 44 breast screening centres for 1 year (On the basis that in England there are 82 centres each screening around 25,000 women per year).

There is no adjustment for drop out or crossover because once the intervention is applied to a screening centre each batch will automatically be randomly assigned to intervention or control groups by the NBSS computer system, and the intervention applied automatically by that same system. A woman could be lost to follow up if she is recalled from screening for further tests and does not attend her follow up appointment, however this is uncommon and so we have assumed low dropout rates for those who are recalled for further tests.

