## Analysis 2:

The second model will adjust for other predictors of cancer detection in order to correct for any imbalances in these between intervention and control group.

First a model will be constructed with known predictors of cancer detection rate. The woman's age and whether she has previously attended screening are known to affect cancer detection rate and so will be included in the model as fixed effects. Then screening centre and batch will be tested for inclusion as levels in the model, using the same process as analysis 1. The treatment will be added to this baseline model.

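### Batch, the unit of randomisation, stays in the model only if it passes a 5% Wald test; the likely inflation of type I error is small, but batch should be kept by design.

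*Combined protocol and SAP*

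**What the plan says.** Protocol section 2.1 defines the cluster: "A cluster for randomisation is a batch of mammograms". Protocol section 3.4 adds that randomisation is at batch level within each centre. SAP section 2 accepts the consequence, stating that "as randomisation occurs at the batch level, collected data is clustered and must also be taken into consideration", and multiplies the sample size by a design effect of 1.09.

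The analysis sections then make the same level optional. Protocol section 3.4 says: "To prevent over-fitting each level will only be included if they explain a sufficient portion of the variability". SAP section 6, Analysis 1, repeats this: "each level will only be included in the final model if it explains a sufficient portion of the variability and improves model fit". Centre goes in first: "It will be retained in the model if it improves model fit (Wald test at the 5% level, see limitations section". Batch follows: "Then batch will be considered for addition as a level to this model if it improves model fit according to the same criteria". Analysis 2 does the same: "Then screening centre and batch will be tested for inclusion as levels in the model, using the same process as analysis 1". SAP section 7 uses the primary-analysis methods for recall, disagreement, interval cancers and positive predictive value (PPV).

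No section keeps batch regardless of the test, and none names a cluster-robust standard error as a fallback. The sufficient share of variability has no threshold, and the limitations section that the rule points to is not in the SAP's contents list.

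**The concern.** Women in the same batch share an allocation. Whether their outcomes are correlated is a feature of the design and the population, and a non-significant variance test does not show that the correlation is absent. If batch is removed while its variance is above zero, the treatment standard error is too small, the interval too narrow and the type I error above 5%. A retained centre level does not help, because both arms are present in every centre and the correlation at issue lies between women of one batch.

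The reason given, over-fitting, carries little weight: one variance parameter is estimated from about 27,000 batches. The test is also made at the boundary of the parameter space (a variance cannot be negative), where a Wald test is conservative and leans towards dropping the level.

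What matters is how often the rule would drop batch, and how much clustering would be present when it did.

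**Working it through.** **1. The plan's own figure.** Inputs from protocol section 4 and SAP section 2: 7.8 against 8.3 per 1000, and "for a two-tailed test at 80% power and 5% significance, 501,361 women are required in each arm". The standard two-proportion formula with pooled variance and no continuity correction gives 501,398 per arm, which agrees. Then 2 × 501,361 × 1.09 = 1,092,967, against 1,093,780 stated, which also agrees. The stated ICC and batch size give DE = 1 + 39 × 0.002 = 1.078 rather than 1.09. That is a separate point, and both values are carried below.

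**2. Harm if batch is dropped.** True two-sided type I error = 2 × [1 − Φ(1.96/√DE)]; shortfall in the standard error = 1 − 1/√DE.

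| DE | Type I error | SE too small by |
|---|---|---|
| 1.058 (batch of 30, as in protocol 2.1) | 5.7% | 2.8% |
| 1.078 | 5.9% | 3.7% |
| 1.09 | 6.0% | 4.2% |

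**3. Chance that the rule keeps batch.** With k batches of m women, SE(ICC) ≈ √[2/(k·m·(m−1))], and the probability of retention ≈ Φ(ICC/SE − 1.96). In the full data k = 1,093,780/40 ≈ 27,345 and m = 40, so SE = 0.000217. At ICC 0.002, z = 0.002/0.000217 ≈ 9.2 and retention is about 100%. A beta-binomial simulation of a moment estimator (400 runs per ICC value) gave a null standard deviation of 0.00022, and retention of 100% at ICC 0.002, 98–99% at 0.001, 53% at 0.00043 and 15–17% at 0.0002.

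**4. Both together.** Overall type I error ≈ (probability kept) × 5% + (probability dropped) × (type I error if dropped), treating the level test and the treatment test as independent. In the full data:
- Keeping and dropping are equally likely at ICC = 1.96 × 0.000217 ≈ 0.0004. There DE = 1.017, the SE is 0.8% too small and type I error if dropped is 5.2%.
- The overall rate peaks at about 5.1%, near that ICC.

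**5. Smaller analyses at ICC 0.002**, if the rule is re-applied in them. The documents do not give the share of batches that are first of the workday for both readers; 5% and 20% are assumptions.

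| Analysis | k, m | Batch dropped | DE | Type I error if dropped |
|---|---|---|---|---|
| First batch of workday, 5% of batches | 1,367, 40 | 46% | 1.078 | 5.9% |
| First batch of workday, 20% of batches | 5,469, 40 | about 2% | 1.078 | 5.9% |
| First or last five cases | 27,345, 10 | 40% | 1.018 | 5.2% |

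Over all ICC values, the overall rate for the 5% subgroup peaks at about 5.4%.

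**6. PPV.** Protocol section 1.1 gives 8 cancers and 36 false-positive recalls per 1000, so 40 × 0.044 ≈ 1.8 recalled women per batch. No ICC for PPV is given; I assume 0.002. With equal batches, DE = 1 + 0.8 × 0.002 = 1.0016. If recalls per batch vary as a Poisson count, DE ≈ 1 + 1.76 × 0.002 = 1.0035. Batch would usually be dropped (about 95% of the time with equal batches), but type I error is then 5.02% to 5.04%. At an assumed ICC of 0.01 and Poisson counts, DE ≈ 1.018 and type I error is about 5.2%.

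**7. What was reported.** Supplement 3 gives a batch variance for detection of 0.811 (0.757–0.866). Its SE is (0.866 − 0.757)/3.92 = 0.0278, so z ≈ 29. Batch was retained at p<0.001 for detection, recall and disagreement.

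**The case against.** The strongest defence is that the rule limits its own damage. Batch is likely to be dropped only when there is little clustering to correct. At even odds of retention, DE − 1 = 1.96 × √[2(m−1)/(k·m)], which is at most 1.96 × √(2/k), or 0.017 for 27,345 batches, whatever the batch size. This stands, and it is why the consequence is small in the full data, in the first-or-last-five subgroup and for PPV. It protects less when k is small: for 1,367 batches the same bound is 0.075.

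It is also fair that Analysis 1 lists the subgroup analyses without saying that level selection is repeated in them, so the subgroup risk is conditional on that reading.

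A reader might infer more than the documents support:
- **A type I error of 9% or more.** Omitting batch at a variance of 0.811 would give an approximate DE of 1.40 and a type I error near 9.7% (assuming batches of 40 and 8.05 cancers per 1000). But with z near 29 the rule would not drop batch at that variance.
- **That the reported results are compromised.** Supplement 3 shows batch kept in every model it reports.
- **That all women would be treated as independent.** If only batch is dropped, the centre level can remain.
- **That centre must also be forced in for this reason.** With randomisation within centre, dropping centre does not produce this inflation.

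**Conclusion.** The plan contradicts itself: SAP section 2 requires batch clustering to be handled, while protocol section 3.4 and SAP section 6 let a significance test remove it, with no fallback. Dropping batch can only understate the treatment standard error when batch variance is above zero.

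The size is modest. For the main analysis, overall type I error peaks at about 5.1%, and the reported detection, recall and disagreement models are unaffected. The largest exposure found is the first-batch-of-the-workday subgroup, with an overall peak of about 5.4% if it holds 5% of batches and the rule is re-applied there. For the first or last five cases and for PPV, type I error would be about 5.0% to 5.2% when batch is dropped.

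These figures rest on batches of 40, an ICC of 0.002 where one is needed, a normal approximation to the Wald test, and the assumed subgroup shares. Supplement 3 shows no model for that subgroup, for PPV or for interval cancers, so for those analyses the documents leave the handling of clustering to the test.

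**What to change.** In protocol section 3.4 and in SAP section 6, Analyses 1 and 2, state that a random intercept for batch is kept in every primary, secondary and subgroup model whatever its significance. Add that, if the batch variance is estimated at zero or the model does not converge, standard errors robust to clustering by batch will be used. Any significance test of a level may apply to centre only. Have SAP section 7 refer to this rule, so that it covers PPV and the interval-cancer analysis, which awaits a separate extraction. Remove the pointer to the limitations section, or supply that section.

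The cost is a few sentences and slightly wider intervals in some sparse analyses. The sample size is unchanged: it already includes a design effect of 1.09, and power at 1,093,780 women with batch kept is 80.0%.

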#### 1.2 Existing knowledge

In the NHSBSP, each set of mammograms is read by two radiologists who each indicate if there should be a recall for further tests. Disagreements are referred for arbitration, usually by a third radiologist. Radiologists assess two mammograms per minute on average which equates to 120 in a 1-hour session. This is a highly skilled, pressurised but repetitive and frequently intellectually unchallenging activity. A vigilance decrement of performance decrease over time has been observed in similar repetitive visual tasks such as radar operator.

Data from an observational study using the Breast Screening Programme database for eight English breast screening centres for 3 years has shown that the probability of being recalled for further tests and of having cancer detected at screening is dependent on the time since the radiologist had a break from reading. For the first ten cases after a first reader break, the cancer detection rate for the whole process (including second reader and arbitration) is higher. These extra cancers detected are not associated with a higher probability of being DCIS rather than invasive, and have a similar mix of grades 1, 2 and 3 to the rest of the cancers detected at screening so this phenomenon is unlikely to be associated with increased overdiagnosis.

First and second readers read each batch of mammograms in the same order, thus their postbreak increases in cancer detection rate occur when reading the same women's mammograms.

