### Subgroups for subgroup analysis

The following variables will be used to construct subgroups for analysis (see section 8 for more details).

- Woman's age in groups: 52 and under, 53-59, 60 and over
- Case position in batch [number of cases from either the beginning or end of the batch, whichever is smaller], with extra column dichotomising into 'first or last five' and 'other'.
- Whether the batch was read first in a workday by both readers [calculated by whether another batch was read by the same reader that day for both readers]

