#### 8. Other analyses with same data set

- Performance with number of cases since the beginning of the batch. [R1intendedOrder]
- Effects on performance of reader completing one session after another and with time of day [Calculate batch in day by assigning a clinic start time for each reader using date and time stamp for first case read for each ReportingSetID].

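### The Analysis 1 subgroups have no stated treatment-by-subgroup interaction test, and the derivation of first batch of the workday, read literally, selects only single-batch days

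*Combined protocol and SAP*

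**What the plan says.** Protocol section 3.4 announces subgroup analyses in younger women and in cases at the beginning or end of the batch. Its reason is that the intervention may work better in those groups.

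SAP section 6, Analysis 1, carries this forward as "A sub-analysis of those cases which are intended to be read in the first or last 5 of the batch", together with three age groups (52 and under, 53-59, 60 and over) and the first batches read in a workday by both readers. It does not say how the subgroups will be compared.

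SAP section 3, under the subgroup variables, splits batch position into the first or last five cases and the rest. It derives the first-batch variable as follows: "calculated by whether another batch was read by the same reader that day for both readers". It refers the reader to section 8 for details, but section 8 does not describe these subgroups. What section 8 does contain, for other analyses, is a time-stamp rule: "Calculate batch in day by assigning a clinic start time for each reader using date and time stamp for first case read for each ReportingSetID".

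Treatment interactions appear only in Analysis 3. Its list includes distance from the nearer end of the batch and whether the batch was read immediately after another. Terms are kept at the 10% level, and the analysis is labelled exploratory and excluded from the main paper. Age enters only through the baseline model and is not on the list of predictors whose interactions are considered. First batch of the workday is not on the list either.

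**The concern.** A subgroup chosen because the effect may be larger there raises a question about a difference between groups. Separate estimates and p-values do not answer it. An effect can reach significance in one group and miss it in another only because the groups differ in size. The batch-end group holds 25% to 33% of the women, so this will happen often.

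These subgroups are where the plan looks for the effect its theory predicts. Without a stated interaction test, a reader of the main paper has nothing pre-specified against which to judge a claim, positive or negative, about batch ends, age or first batches.

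The first-batch variable has a further problem. The subgroup is meant to hold the first batch of the day, but the derivation asks whether the reader read another batch that day, not an earlier one. A programmer who followed the words would drop the true first batch of every multi-batch day.

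**Working it through.** **Inputs.** Detection rates of 7.8 and 8.3 per 1000, two-sided 5%, 80% power, 501,361 women per arm, design effect 1.09 and total 1,093,780 (protocol section 4 and SAP section 2). Batch size is 40 (SAP section 2: "using the derived ICC of 0.002 and a cluster (batch) size of 40 women") or about 30 (protocol section 2.1). A reading session is two cases per minute, "which equates to 120 in a 1-hour session" (protocol section 1.2).

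**1. The plan's own figure.** The sum of the two binomial variances is 0.0078 × 0.9922 + 0.0083 × 0.9917 = 0.01597. Then n per arm = (1.960 + 0.842)² × 0.01597 / 0.0005², about 501,400, against 501,361 stated. Inflating, 2 × 501,361 × 1.09 = 1,092,967, against 1,093,780 stated. The plan's figures are reproduced closely. A batch of 40 with ICC 0.002 gives 1 + 39 × 0.002 = 1.078, not 1.09. The stated 1.09 is used below; 1.078 changes each result by less than one percentage point.

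**2. Separate tests under a uniform effect.** Assume a gain of 0.5 per 1000 everywhere, a control rate of 7.8 per 1000 in both groups, and near-independent tests. For a batch of 40, the first and last five cases are 10/40 = 25% of the women.

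- Batch ends: 1,093,780 × 0.25 / 2 = 136,722 per arm; divided by 1.09, 125,433. SE = √(0.01597 / 125,433) = 0.000357; z = 0.0005 / 0.000357 = 1.40; power = Φ(1.40 − 1.96) = 0.288.
- Other cases: 1,093,780 × 0.75 / 2 = 410,168 per arm; divided by 1.09, 376,300. SE = 0.000206; z = 2.43; power = Φ(2.43 − 1.96) = 0.680.
- Exactly one significant: 0.288 × 0.320 + 0.680 × 0.712 = 0.576, about 58%.

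For a batch of 30, the powers are 0.366 and 0.629, and exactly one is significant about 53% of the time. With no effect at all, the figure is 2 × 0.05 × 0.95 = 9.5%. An interaction test at the 5% level would be falsely positive about 5% of the time in each case.

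**3. Number of tests.** Five subgroup tests at 5% (batch ends, three age groups, first batch) give 1 − 0.95⁵ = 22.6% chance of at least one false positive if there is no effect and the tests are independent.

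**4. First batch of the workday.** A session of 120 cases is 120/40 = 3 batches, or 120/30 = 4. Under the literal rule, no batch in such a session qualifies, not even the true first one. The documents do not give the share of reader-days with a single batch. Call it q, assumed independent between the two readers. The rule then keeps q² of the batches that are first for both: 6%, 25% and 56% for q = 0.25, 0.50 and 0.75.

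**5. Five cases against ten.** Protocol section 1.2 reports: "For the first ten cases after a first reader break, the cancer detection rate for the whole process (including second reader and arbitration) is higher". The SAP cuts at five and gives no reason. In a batch of 40, five at each end is 25% of cases and ten at each end is 50%.

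**The case against.** The plan nowhere says that a difference in effect will be inferred by comparing subgroup p-values. Analysis 1 says only that sub-analyses will be done, and does not explicitly plan a test in the non-edge cases. Interactions with batch position and consecutive reading are planned, and Analysis 3 was agreed on 20/3/2014, before the first data were collected on 23/10/2014. All of this is correct. A reader might infer that the plan intends a fallacious comparison, and the documents do not show that. What stands is that no test is stated for the Analysis 1 subgroups, and that Analysis 3 does not fill the gap for age or first batch, or for the main paper.

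On first batch, the bracket may be shorthand for an earlier batch, since the variable's own label says the batch was read first. A reader might infer that the subgroup was in fact misclassified. The documents do not show how it was programmed, so the finding is an ambiguity in which the literal reading contradicts the label.

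A reader might also infer that the five-case window is an error and that it triples the number of women needed. The documents do not support this. The figure assumes a flat effect over ten cases and none beyond, and the protocol gives no such shape. For a batch of 40, a flat ten-case effect seen through the five-case window gives a z ratio of (0.667/√5.333) / (1/√4) = 0.577. An effect confined to the outer five, seen through a ten-case window, gives (0.5/√4) / (1/√5.333) = 0.577, the same loss. Ten at each end would also leave only ten other cases in a batch of 30, and none in a batch of 20 or fewer. The SAP also keeps the full position count, with the dichotomy as an extra column.

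**Conclusion.** The point holds for the missing interaction tests and, on the literal text, for the first-batch derivation. At the plan's own effect size, separate tests at the batch ends and elsewhere would disagree about 58% of the time for batches of 40 and 53% for batches of 30, with no true difference. These figures assume a uniform gain of 0.5 per 1000, equal control rates and near-independent tests. They fall towards 9.5% as the true effect approaches zero. The loss in the first-batch subgroup depends on an unreported share of single-batch days, and the 6% to 56% range is illustrative.

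The five-case cut is unexplained against the first-ten-cases evidence, but it is a valid pre-specified choice. A reader might also take the primary result to be in doubt. It is not: the primary model has treatment as its only predictor and does not use these subgroups. Nor does the supplied supplement report any result for the Analysis 1 subgroups.

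**What to change.** - For each Analysis 1 subgroup variable (batch end, age group, first batch), fit one model on all women, with the same levels as the primary model plus the subgroup and a treatment-by-subgroup term. Use a joint test for the three age groups.
- Report the interaction estimate and p-value, with stratum estimates and confidence intervals. Base any claim that the effect differs on the interaction alone. A non-significant interaction should not be read as proof of equal effects.
- Define first batch as the earliest time-stamped batch of that day for each reader, required for both, using the rule already in SAP section 8. Correct the cross-reference from section 3.
- Give a reason for the five-case cut. At most, add a sensitivity analysis with ten cases or with continuous position.

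The cost is a few lines of SAP text, one recoded variable and three extra model fits. No new data are needed: the SAP already lists distance from the nearer batch end and uses the reading time stamps. Because the supplement already reports treatment results, anything added now should be labelled post hoc.
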